#### Pyogenic Granuloma

Pyogenic granulomas occasionally develop after trichiasis surgery, and it is thought that these are a response to a foreign body, such as suture material or a jagged incision edge. The patient examiners will evaluate presence of granulomas at 3-6 months and 12 months. All granulomas will be noted, regardless of size.

## 4. STUDY DESIGN

## 4.1 Overall Design

This study is a randomized controlled trial comparing two surgical procedures for the management of post-operative trichiasis. Individuals are eligible if they have at least one eye with post-operative trichiasis. Participants are identified either from the MTSS cohort at the MTSS 12 month visit or from screening patients for PTT using surgical logs from existing country programs throughout the three regions and/or conducting screenings during household visits. Individuals will be consented and enrolled on the day they have surgery. We will enroll up to 936 individuals and randomize them on a 1:1 basis to surgery with BRAP or surgery with Trabut. They will be followed for 12 months to assess development of repeat post-operative trichiasis and eyelid contour abnormality.

## 4.2 Scientific Rationale for Study Design

The BRAP has been used in two countries and initial study outcomes are excellent. A larger, randomized study is required to determine whether BRAP is superior to Trabut.

## 4.3 End of Study Definition

Each study participant reaches the end of the study at 12 months after surgery.

## 4.4 Data Collection and Management

Data will be collected primarily electronically through customized Open Data Kit (ODK) forms on Motorola Moto X Pure Edition, Samsung S8, and Samsung A9 phones. At the end of each day, data from the phones will be downloaded to a customized Access database. The Access database will be stored on a UNC approved, encrypted laptop. Both the laptop and the database will include password protection. Each week, the project director will transfer accumulated data to the UNC Coordinating Center. This transfer will be done via a secure File Transfer Protocol (FTP) connection.

All data will be collected by trained staff members who have completed human subjects' research training.

Data will primarly be collected on encrypted mobile phones. All devices will be encrypted and password protected. They will be stored in locked offices each night.

Adverse events (AE) will be monitored throughout the study. At surgery, the data collection form will have specific questions regarding each of the possible adverse events that could happen during surgery (excess bleeding, division of the eyelid margin). If an event is encountered, the project director will report it to FMHACA in writing, within 48 hours of occurrence of the event according to the authority guideline, and to the PI ([name]) within 72 hours. This report will include measures taken to mitigate the event. At the 2-week and 3-6 month and 12 month visits, deaths and

hospitalizations will be proactively collected (the data collector will ask the participant if they have been hospitalized; death will be noted if a family member reports the participant has died). Any AEs occurring at these visits will be reported to the Coordinating Center within 72 hours. At all visits, deaths will be noted and reported to the Coordinating Center within 72 hours. Whenever an AE is reported to the Coordinating Center, [name] will assume responsibility for sharing with the appropriate parties. If an event could possibly be related to the study treatment, she will share the details of the event with the study monitor, who will review the data in a masked fashion to determine whether it could be related to the study procedure. He also monitors all aspects of the study assuring Good Clinical Practice (GCP) of the trial. Therefore, he will have responsibilities with direct accountability to the sponsor with periodic monitoring, reporting the findings to the sponsor. We will follow the Data and Safety Monitoring Board's guidelines on reporting these events to them.

## 5. STUDY POPULATION

Participants will be recruited from three regions in Ethiopia: SNNPR, Oromia and Amhara. Some participants will be recruited from within the US National Eye Institute (NEI) funded clinical trial of incident trichiasis surgeries, the Maximizing Trichiasis Surgery Success (MTSS) Trial, currently taking place in SNNPR. Other non-MTSS post-operative trichiasis (PTT) cases from the 3 regions will also be recruited. All individuals with PTT in at least one eye, aged >18 years, and living in the area will be eligible to participate. We aim to enroll 936 individuals during the 2019-2020 surgical campaigns being supervised by Orbis International, The Carter Center and the Fred Hollows Foundation. The Carter Center will be responsible for the screening and identification of patients in Amhara, while the Fred Hollows Foundation will be responsible for conducting screening in Oromia.

We will not exclude subjects based on race or gender.

#### 5.1 Subject Inclusion Criteria

In order to be eligible to participate in this study, an individual must meet all of the following criteria:

- Aged 18 or older
- At least one eyelid with post-operative upper eyelid trichiasis needing surgery
- Willing to comply with all study procedures and be available for the duration of the study

## 5.2 Subject Exclusion Criteria

Any individual who is unable to provide informed consent will be excluded from participation in this study.

## 5.3 Strategies for Recruitment and Retention

Subjects will be identified on the day that they present for their 12-month follow up visit for the MTSS Trial in the SNNPR region or from surgery logs from programs conducting village-based screening in all three regions. List of patients previously identified to have PTT during survey activities or programmatic follow-up activities may be consulted to determine potential study candidates. Trained case finders may also be used to conduct house-to-house visits to identify potential study candidates. Patients found to have post-operative trichiasis in at least one upper eyelid that had surgery performed in the MTSS Trial will be eligible to have repeat surgery performed as part of the PTT trial. Patients suspected of having PTT (and thus may be eligible for the study) will be assessed by surgeons to confirm eligibility. Surgery will not be performed that day. Instead, the team will schedule surgery days for that district after determining how many patients in the area have PTT of sufficient severity to warrant surgery. All recruitment and screening activities will be conducted by the coordinating partner in that region—The Carter Center in the Amhara Region, the Fred Hollows Foundation in Oromia, and Orbis in SNNPR.

On the day of surgery, an examiner will visit the patient and discuss the study as well as the opportunity to have repeat surgery. If the patient agrees to repeat surgery s/he will be brought to the surgery site where she will meet with a consent specialist who will provide a full description of the study and will complete the consent process if the patient is eligible and interested.

All repeat surgery trichiasis patients will receive surgery free of charge, regardless of participation in the trial. If a patient has patient has bilateral post-operative trichiasis and elects to have surgery on both eyes, both eyes will be enrolled in the study. Patients that are not eligible for the study but are presenting with TT will be offered surgery at no cost by the program staff of the coordinating organization.

Subjects will not receive compensation for participation. Participant retention is maintained through contact with a local community health worker, who lives in the village with the participants and has a long-term relationship with them. The project director will call community health workers approximately 2 weeks before upcoming study visits to remind them that they need to contact the subjects living in their village to bring them for the follow up visit. Also, during the surgery day and at each follow up, patients will receive reminder cards stating the date and location of the next follow up visit. This approach has been extremely successful in our previous trials, with retention rates of over 95% of eligible subjects.

#### 6. STUDY INTERVENTION

#### 6.1 Study Intervention Description

Participants will undergo either the Trabut procedure or the BRAP. Both procedures are performed under local anesthesia.

#### 6.1.1 Trabut

The Trabut procedure is the WHO-recommended standard surgical procedure used for initial trachoma trichiasis surgeries and is also widely used for PTT. The eyelid is fixed on the Trabut plate and an incision 3 mm from the eyelid margin is made through the conjunctiva and tarsal plate, without cutting the orbicularis muscle. The muscle is dissected from the tarsal plate in both fragments, and the fragments are re-sutured so that the eyelid margin is rotated outwards and the eyelashes no longer touch the globe. For further details, refer to the WHO Yellow Manual.

#### 6.1.2 **BRAP**

#### **Beveled Incision**

[figure not shown]
A Trabut plate is used to evert the upper eyelid in the standard fashion for Trabut surgery. (Fig. 1A, and Fig. 22 and 23 in yellow manual). A caliper is used to measure 3 mm ("C" in Fig. 2C) superior to the eyelash follicles on the conjunctiva across the width of the eyelid. The sharp point of the caliper or the scalpel blade can be used to make small scratches in the conjunctiva to delineate this position. This often corresponds to the scar or a portion of the scar from the original TT surgery ("scar" in Fig. 2B). A scalpel is used to make a tarsal incision along the marked position, beveled towards the eyelash follicles with care not to cut the follicles (the incision is the line between "B" and "D" in Fig. 2). Note that this beveled incision is in contrast to the typical Trabut incision that is made perpendicular to the plane of the upper evelid tarsus. Upon completion of the tarsal incision, sharp dissection between the scarred orbicularis and the scarred and thickened proximal tarsus is performed (Fig. 2D). White scar contributing to an eyelid contour abnormality is resected (Fig. 2E), and dissection is continued between the orbicularis and tarsus to the top of the tarsus (Fig. 2D). After dissection and release of the scar from the original TT surgery, the contour of both the beveled, distal fragment and the larger, proximal fragment should be normalized (Fig. 1B) The Trabut clamp and traction suture are removed.

#### Rotation and Advancement

[figure not shown]
The beveled fragment is then externally rotated (Fig. 2D), and the proximal tarsal fragment is advanced downward (Fig. 1C, Fig. 2E). The cut edge of the beveled distal fragment is positioned 1 mm above the cut edge of the proximal fragment (Fig. 2F).

#### **Suturing**

If excess upper eyelid skin noted, a horizontal mattress suture (the "high" suture) is placed through the skin 10 mm above the lash line as the approximate position of the upper eyelid crease and through Muller's muscle just above the top the upper tarsus using 5-0 polyglactin 910 (Fig. 2F). Although, this suture is not tied until the end of the procedure, it is important to check that it is placed properly and does not undo the advancement when it is tightened. The relative position of the tarsal fragments is stabilized with horizontal mattress sutures as follows. Starting centrally, the suture is placed backhand from just above the lash line, through the distal fragment, and through the proximal tarsal fragment. The needle is repositioned in the standard forehand position, and the suture is advanced horizontally by 3 mm and is placed thorough the proximal tarsus, through the distal fragment, and exiting just above the lash line. At least 2 additional sutures are placed in the same fashion, nasal and temporal to the central suture. The 3 sutures can be placed for optimum contour if necessary. The "high" suture is then tied (Fig. 2F).

**Figure 1. Initial steps of BRAP.** A) Eversion of the upper eyelid with an eyelid contour abnormality over a Trabut plate. B) Upper eyelid after completion of the beveled incision, release and removal of the scar tissue, and normalization of the eyelid contour abnormality. C) Demonstration of ability to advance the proximal tarsal fragment, confirming adequate dissection.

**Figure 2. BRAP**. A) Sagittal view of an upper eyelid immediately after Trabut surgery. B) Appearance of the upper eyelid after healing from Trabut surgery showing thickened tarsus in the region of the scar and recurrence of the entropion and post-operative trichiasis. C) A beveled incision through the tarsus is made along the line between B and D. The incision is continued superiorly between the orbicularis and tarsus to the top of the tarsus (arrow). D) Scar tissue in the region of the prior surgery (gray shading circled by dashed line) is identified and removed if needed. The distal fragment is externally rotated (large arrow). E) The larger proximal tarsal fragment in advanced downward and the smaller, rotated, distal fragment is recessed upwards. F) The cut edge of the beveled distal fragment is positioned 1 mm above the cut edge of the proximal fragment. The advancement is stabilized with three horizontal mattress sutures (lower suture) placed nasally, centrally and temporally. If needed, an additional horizontal mattress suture is placed centrally from the approximate upper eyelid crease (10 mm) to Mullers' muscle (higher suture).

We believe that BRAP may have more success than currently available TT surgery procedures because the margin fragment is recessed away from the eye creating more distance between the trichiatic lashes and the cornea. Additionally, the beveled incision creates a marginal fragment that is thinner and more uniform in thickness than the fragment created in an eyelid with PTT by the Trabut or BLTR procedures, making it easier to rotate, recess and stabilize during the healing period.

#### 6.2 Randomization Procedures

Participants will be randomized at the participant level on a 1:1 basis to one of two arms: 1) the BRAP procedure or 2) the Trabut procedure. If both eyes need surgery, they both will have the same procedure performed. [name] will oversee generation of the randomization assignments at UNC. We will utilize random, permuted blocks of varying sizes to ensure balance between arms on a frequent basis.

Randomization assignments will be prepared by UNC staff in Chapel Hill, in individual opaque envelopes with the patient ID number on both the outside of the envelope and on the internal papers indicating the arm assigned.

Randomization will occur on the day of surgery in order minimize chances of randomizing an individual who does not present for surgery.

The envelope will be opened in the surgery room by the surgical assistant. The surgeon and surgical assistant will both confirm verbally with one another the assigned surgical procedure at the start of the procedure. They will be required to indicate the assigned procedure on the surgical evaluation form as well as the procedure they ultimately perform.

The randomization assignments will be developed at UNC. After each surgical outreach camp period, reported assigned surgical procedures will be compared against the master table to ensure the assigned procedure is consistently being reported for each participant. Details on monitoring are available in the quality assurance section.

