#### Alternative hypothesis:

1) Surgery performed using the BRAP procedure will result in a relative 30% reduction in the rate of post-operative trichiasis compared to surgery using the Trabut procedure.

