#### 9.2 Sample Size Considerations

The planned sample size for this trial is 700 participants. This sample size will give sufficient power to detect a 30% relative difference in post-operative trichiasis rates between the BRAP and Trabut procedures. This estimate is based on the following assumptions:

- 35% of eyelids in the Trabut group will develop post-operative trichiasis during the 12 months following surgery
- Two-sided alpha error = 5%
- Power = 80%
- 10% loss to follow up

In the event that the number of participants is lower than anticipated, we are still adequately powered to detect a clinically significant difference (see table below). For instance, if only 600 participants enroll, we have 80% power to detect a relative difference of 32%.

	Relative Risk							
Number of Participants	1.2	1.3	1.32	1.4	1.5			
560	44%	72%	77%	91%	99%			
600	47%	75%	80%	93%	99%			
640	49%	77%	82%	94%	99%			
720	53%	82%	86%	96%	99%			
800	56%	85%	89%	97%	99%			

Power to Detect a Difference between Treatment Groups

The subset of 186 participants who enrolled and received surgery prior to August 1, 2019 will be excluded from the primary analysis because they were operated prior to precise standardization of the incision and suture placement. These individuals will continue to be followed and cared for in the same manner as all other study participants.

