## Post-operative Trichiasis Analyses:

The **primary analysis** will be based on the dichotomous outcome: presence or absence of post-operative trichiasis noted at any time point beginning with the 3-6 month visit and within 12 months following surgery (trichiasis noted at either the 3-6 month or 12

month visit will be considered as post-operative trichiasis, regardless of whether there is trichiasis at the final visit). Both unadjusted and adjusted analyses will be performed. Adjusted analyses will account for the severity baseline PTT, with severity defined based on the table below.

Trichiasis Severity Classification	Description
Mild	1-4 Eyelashes touching globe, no epilation
	OR
	< 1/3 of eyelid epilated, no lashes touching globe
Moderate	5-9 Eyelashes touching globe, no epilation
	OR
	1-4 lashes touching globe and < 1/3 of eyelid epilated
Severe	5-9 Eyelashes touching globe and 1-10 eyelashes epilated
	OR
	10+ Eyelashes touching globe, regardless of epilation status
	OR
	>1/3 of eyelid epilated, regardless of lashes touching

(Gower et al. 2013. JAMA Ophthalmol.;131(3):294-301.)

**Multiple secondary analyses** of post-operative trichiasis will be performed. We will compare the severity of post-operative trichiasis between groups, with severity defined using the table above. Additionally, we will assess the frequency of overcorrection performed at the one-day visit.

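### Region and recruitment source are known at randomisation but are not named as covariates for PTT; naming them is a small, nearly free improvement

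*Combined protocol and SAP*

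**What the plan says.** Section 6.2 randomises participants 1:1. On the method it says: "We will utilize random, permuted blocks of varying sizes to ensure balance between arms on a frequent basis". No stratification factor is named, and the section does not say whether the ID lists were divided by region or surgical camp.

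Section 5 recruits from SNNPR, Oromia and Amhara. Some participants come from the MTSS Trial, which runs in SNNPR, and "Other non-MTSS post-operative trichiasis (PTT) cases from the 3 regions will also be recruited". Section 5.3 adds that "All recruitment and screening activities will be conducted by the coordinating partner in that region", with a different partner in each. MTSS cases are found at that trial's 12-month visit; the others come from surgery logs, lists and house visits. Section 10.2 checks identity against the MTSS list or the screening logs when the patient presents for surgery, and section 6.2 randomises that same day. Both factors are therefore known at allocation.

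Section 9.3 plans eye-level logistic models with GEE. For PTT it promises unadjusted and adjusted analyses and does not say which one decides. On the adjusted one: "Adjusted analyses will account for the severity baseline PTT, with severity defined based on the table below". The Protocol Summary says the comparison will also control for demographic characteristics, which it does not list.

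**The concern.** Participants reach the trial by different routes: three regions with three case-finding partners, and either a fixed visit after trial surgery or programme records and house visits with no stated limit on time since first surgery. Section 3.2 attributes the difficulty of repeat surgery to scarring from the first operation and continuing disease, so it is plausible that region and source predict repeat PTT. If they do, an adjusted model without them leaves explainable variation in the outcome and takes no account of chance imbalance between arms on these factors.

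The second issue is specification. The Summary and section 9.3 give different covariate sets, and one is open-ended. Whether region counts as demographic could be settled after the data are seen.

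**Working it through.** **Inputs from the documents.** Section 9.2: "35% of eyelids in the Trabut group will develop post-operative trichiasis during the 12 months following surgery"; two-sided alpha 5%; power 80%; "10% loss to follow up"; 700 participants. Section 9.1: "Surgery performed using the BRAP procedure will result in a relative 30% reduction in the rate of post-operative trichiasis", so 35% against 24.5%, a difference of 0.105. Sections 4.1 and 9.2: 936 enrolled less 186 excluded leaves 750.

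**The plan's own figure.** The two-proportion formula gives 297 per arm, or 316 with continuity correction. Then 2 × 316 = 632, and 632 / 0.9 = 703 after rounding up. The stated 700 is reproduced.

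**Assumed input.** The documents give no PTT rate by region or source. I assume equal-sized groups averaging 35% under Trabut, a risk ratio of 0.7 in every group, one eyelid per participant and 700 × 0.9 = 630 evaluable.

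**Formulas.** With a the Trabut rate and b = 0.7a the BRAP rate in each group, and means taken over groups:

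- Unadjusted variance of the risk difference: (2/630) × [0.35 × 0.65 + 0.245 × 0.755] = (2/630) × 0.4125 = 0.001309.
- Adjusted variance: (2/630) × [mean a(1−a) + mean b(1−b)] + [mean (a−b)² − 0.105²]/630.
- Power: Φ(0.105/SE − 1.96).

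Worked case, 25/35/45%: mean a² = 0.12917, so mean a(1−a) = 0.22083 and mean b(1−b) = 0.245 − 0.49 × 0.12917 = 0.18171. The last term is (0.09 × 0.12917 − 0.011025)/630 = 0.0006/630. The adjusted variance is 0.001279, a ratio of 0.977. Power goes from Φ(2.902 − 1.960) = 82.7% to Φ(2.936 − 1.960) = 83.6%.

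| Assumed Trabut rates | Variance reduction | Power, unadjusted to adjusted | Equivalent extra participants |
|---|---|---|---|
| 35/35/35% | 0% | 82.7 to 82.7% | 0 |
| 30/35/40% | 0.6% | 82.7 to 82.9% | 4 |
| 25/35/45% | 2.3% | 82.7 to 83.6% | 15 |
| 20/35/50% | 5.3% | 82.7 to 84.6% | 35 |
| 15/35/55% | 9.3% | 82.7 to 86.2% | 65 |
| 25/35/35/45% (region by source) | 1.8% | 82.7 to 83.3% | 11 |
| 20/30/40/50% (region by source) | 4.4% | 82.7 to 84.3% | 29 |

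With 750 × 0.9 = 675 evaluable, the variance reductions are the same; power starts at 85.2% and reaches at most 88.4%.

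**In the planned logistic model** (4,000 simulated trials per scenario, without and with region):

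| Rates | SE of log OR | Mean log OR | Power |
|---|---|---|---|
| 35/35/35% | 0.177 to 0.178 | −0.505 to −0.507 | 82.2 to 82.3% |
| 25/35/45% | 0.177 to 0.180 | −0.515 to −0.528 | 82.0 to 82.6% |
| 20/35/50% | 0.177 to 0.183 | −0.509 to −0.539 | 82.4 to 83.6% |

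The standard error rises. Power rises because the conditional log odds ratio lies further from zero.

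**Increment over the actual plan.** These comparisons start from no adjustment, whereas section 9.3 already adjusts for severity. In simulation with severity in the model, the extra power was about 0 points at equal or 30/35/40% rates, 0.2 at 25/35/45% (within simulation noise), and about 1.5 at 20/35/50% or at four region-by-source groups of 15/30/45/50%. How strongly severity predicts repeat PTT is also an assumption.

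**Cost in parameters.** Two for region and one for source, against 630 × (0.35 + 0.245)/2 = 187 expected events.

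**The case against.** The strongest reply is that this is a covariate preference with an assumed benefit. No rates by region or source are given, the gain at modest spreads cannot be told from simulation noise, and severity may already absorb part of any difference in case mix. This stands, and it sets the size of the point.

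It may also be partly handled. The Summary's demographic characteristics could include region, and varying blocks with surgery scheduled district by district may give approximate regional balance. The documents settle neither. Source is named nowhere as a covariate. The change would also leave the unadjusted analysis as it is.

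Three stronger readings are tempting, and the documents do not support them:

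- *Adjustment would give a narrower odds-ratio interval.* The log-OR standard error rises slightly in the planned model.
- *Loss to follow-up that varies by region undermines the complete-case result.* Take rates of 20/35/50% and losses of 0/5/25% in both arms. The observed Trabut rate is (0.20 + 0.95 × 0.35 + 0.75 × 0.50)/2.70 = 33.6% and the BRAP rate is 0.7 times that, 23.5%. The risk ratio stays at 0.70 and the odds ratio moves only from 0.603 to 0.608. Material bias would need loss that differs by arm, and sections 5.3 and 7.2 state no regional difference in tracing.
- *Source is separable from the operating surgeon.* The documents do not say how surgeons were distributed over sources. MTSS runs only in SNNPR, so source can vary only there.

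**Conclusion.** The point holds as a low-impact improvement. Region and source are known at randomisation, are not stated as strata, and are not named in the PTT model; the Summary and section 9.3 do not give the same covariates. The likely gain is roughly 0 to 1.5 power points beyond severity adjustment, and zero if rates do not differ. This rests on assumed regional and source rates, a constant risk ratio of 0.7, one eyelid per participant with no between-eye correlation, and an assumed effect of severity.

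A reader might infer that the absence of strata makes the trial invalid or biased. It does not: allocation is random, and chance imbalance is covered by the test's type I error. The firmer reason to act is that the covariate list is not fixed.

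**What to change.** In section 9.3, under the PTT analyses, name region (SNNPR, Oromia, Amhara) and recruitment source (MTSS or non-MTSS) beside baseline severity in the adjusted GEE logistic model. Make the Protocol Summary and section 9.3 give the same list: either name each demographic characteristic or remove the phrase. Report a standardised (marginal) risk difference from that model with its confidence interval, since any precision gain appears there and not in the odds-ratio interval.

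The cost is a few lines of wording, no new data, and up to three extra parameters. Randomisation need not change.
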